4.9. Statistical/Analytical Issues

4.9.1. Adjustments for Covariates

No adjustments for covariates are planned.

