Name of Active Ingredient:	daxibotulinumtoxinA										
Title of Trial:	A Phase 3, Randomized, Double-Blind, Placebo Controlled, Multi-Center Trial to Evaluate the Efficacy and Safety of DaxibotulinumtoxinA for Injection to Treat Moderate to Severe Glabellar Lines (SAKURA-1)										
Trial Center(s):	Up to 15 centers in the United States (US)										
Number of Subjects Planned:	Approximately 300 subjects will be enrolled										
Trial Period:	Up to 38 weeks, including 2 weeks for screening										
Phase of Development:	3										
Objective:	To evaluate the efficacy and safety of a single treatment of DaxibotulinumtoxinA for Injection for the treatment of moderate to severe glabellar lines compared to placebo.										
Design and Methodology:	
This is a Phase 3, randomized, double-blind, placebo-controlled, multi-center trial. Approximately 300 adult subjects with moderate to severe glabellar lines will be enrolled. Subjects will be randomly assigned in a 2:1 ratio to DaxibotulinumtoxinA for Injection 40 U or placebo.
 
All subjects will be followed for at least 24 weeks post-treatment for efficacy and safety assessments. If both Patient Frown Wrinkle Severity (PFWS) and Investigator Global Assessment Frown Wrinkle Severity (IGA-FWS) scores at maximum frown, return to baseline by the Week 24 visit or at a visit between Weeks 24 and 36, the visit at which that score is recorded will be the Final Evaluation Visit for the subject.
 
After the Final Evaluation Visit, all qualified subjects will have the option to enroll into an open-label, trial to evaluate the long-term safety of repeat use of DaxibotulinumtoxinA for Injection for the treatment of moderate to severe glabellar lines.
 
The Investigator, trial center staff, subjects, and Sponsor will remain blinded to study treatment throughout the trial. Only the statistician responsible for the randomization codes will be unblinded to the treatment assignments.
										

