Test Article, Dose and Mode of Administration:	DaxibotulinumtoxinA for Injection, 40 U, intramuscular injection, 0.5 mL
Control, Dose and Mode of Administration:	Placebo: DaxibotulinumtoxinA placebo, intramuscular injection, 0.5 mL
Statistical Analyses:	
Primary Efficacy Endpoints
 
Primary clinical efficacy will be assessed by a blinded evaluator who will grade the severity of the subject’s glabellar lines at maximum frown using the IGA-FWS. Also the subject will grade the severity of their glabellar lines at maximum frown using the PFWS. A responder will be defined as a subject who achieves a score of 0 or 1 (none or mild) and an improvement of at least two points from the baseline score, on both the IGA-FWS and PFWS scales concurrently at Week 4.
 
The Proportion of Responders will be compared between daxibotulinumtoxinA and placebo at Week 4 using the Cochran–Mantel–Haenszel (CMH) test stratified by trial center.
 
[REDACTED]
 
[REDACTED]
 
[REDACTED]
 
[REDACTED]

Name of Sponsor/Company:	Revence Therapeutics, Inc.
Name of Finished Product:	DaxibotulinumtoxinA for Injection
Name of Active Ingredient:	daxibotulinumtoxinA
	
	
Sample Size and Power Considerations	
Estimates of treatment efficacy taken from trial RT002-CL002 show that a sample size of 200 and 100 for DaxibotulinumtoxinA 40 U for injection and placebo, respectively, 	
	

LIST OF ABBREVIATIONS AND DEFINITIONS OF TERMS

Abbreviation	Definition
AE	adverse event
ATC	Anatomical Therapeutic Chemical
BoNTA	botulinum neurotoxin type A
BP	blood pressure
CI	confidence interval
CMH	Cochran–Mantel–Haenszel
CRF	case report form
CRO	contract research organization
CS	clinically significant
ECG	Electrocardiogram
FASE	Facial Age Self Evaluation
FDA	Food and Drug Administration
████	████████████████████
GAIS	Global Aesthetic Improvement Scale
GCP	Good Clinical Practice
GLP	Good Laboratory Practice
GLSS	Glabellar Line Severity Score
HHS	U.S. Department of Health and Human Services
ICH	International Conference on Harmonisation
IEC	Independent Ethics Committee
IGA-FWS	Investigator Global Assessment Frown Wrinkle Severity
IRB	Institutional Review Board
ITT	intent to treat
kDa	Kilodalton
Kg	Kilogram
KM	Kaplan-Meier
MedDRA	Medical Dictionary for Regulatory Activities
mL	milliliter
MRC	Medical Research Council
NCS	not clinically significant
PFWS	Patient Frown Wrinkle Severity
PP	per protocol
PT	prothrombin time
Revance	Revance Therapeutics, Inc.

Abbreviation	Definition

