7.3 TRIAL ENDPOINTS

Unless specified otherwise, all endpoints associated with IGA-FWS, PFWS, GAIS, or Subject's Diary, henceforth will be based on assessments at maximum frown.

Primary Efficacy Endpoint:

The primary efficacy endpoint of the trial is the proportion of responders with the response defined as

- Achieving a score of 0 or 1 (none or mild) and an improvement of at least two points from baseline on both IGA-FWS and PFWS scales concurrently at Week 4

- █ [REDACTED]
- █ [REDACTED]
- █ [REDACTED]
- █ [REDACTED]
- █ [REDACTED]
- █ [REDACTED]
- █ [REDACTED]
- █ [REDACTED]
- █ [REDACTED]
- █ [REDACTED]

Safety Endpoints:

- Frequency, severity and relationship to study drug of treatment-emergent adverse events during the first four weeks post treatment and the overall study duration
- Frequency, severity and relationship to study drug of treatment-emergent serious adverse events during the first four weeks post treatment and the overall study duration

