7.5.1 PRIMARY EFFICACY ENDPOINT

Primary clinical efficacy will be assessed by the blinded evaluator who will grade the severity of the subject's glabellar lines at maximum frown using the IGA-FWS and the subject who will grade the severity of their glabellar lines at maximum frown using the PFWS. A response is defined as achieving a score of 0 or 1 (none or mild) and an improvement of at least two points from the baseline, on both the IGA-FWS and PFWS scales concurrently at the time point of evaluation. With both IGA-FWS and PFWS using a 4-point scale and the target population having a score of 2 or 3 (moderate or severe) at baseline, achieving an improvement of at least two points is inclusive in the status of achieving a score of 0 or 1 (none or mild). Henceforth, the response defined here will be abbreviated as "2-point composite response."

The proportion of subjects who have a 2-point composite response at Week 4 will be compared between daxibotulinumtoxinA and placebo using the Cochran–Mantel–Haenszel (CMH) test stratified by trial center using a two-sided test with a Type I error rate of 0.05.

[REDACTED]

[REDACTED]

[REDACTED]

[REDACTED]

[REDACTED]

[REDACTED]

[REDACTED]

[REDACTED]

- [REDACTED]
- [REDACTED]

[REDACTED]

[REDACTED]

[REDACTED]

- [REDACTED]
- [REDACTED]
- [REDACTED]

[REDACTED]

[REDACTED]

[REDACTED]

- [REDACTED]
- [REDACTED]

[REDACTED]

[REDACTED]

[REDACTED]

- | [REDACTED]
- | [REDACTED]
- | [REDACTED]

[REDACTED]

[REDACTED]

[REDACTED]

- | [REDACTED]
- | [REDACTED]
- | [REDACTED]

[REDACTED]

[REDACTED]

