7.5.5 HANDLING MISSING DATA AND OTHER CONSIDERATIONS

Missing Data

[REDACTED]

[REDACTED] For endpoints that are a composite and/or derived from study assessments, imputation of missing data will be performed on the original assessments first.

No imputations will be utilized for the PP analyses.

As needed, a model-based multiple imputation approach may be explored to assess the impact of different imputation methods on the trial outcomes.

Pooling Data

Most of the efficacy endpoints are analyzed with trial center as a stratification factor. The trial is intended to be conducted in a manner such that a minimum of 5 ITT subjects in each treatment group will be enrolled at each trial center/site. In the event that there are too few subjects in a treatment arm at a single site, this site will be combined with another to achieve the desired minimum sample size per arm.

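### The readable plan does not adjust the primary treatment difference for baseline severity, which the 2-point rule makes likely to be prognostic; adjusting is a small, nearly free gain in precision

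*SAP*

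**What the plan says.** Protocol 7.3 defines a responder as a subject with a score of none or mild and "an improvement of at least two points from baseline on both IGA-FWS and PFWS scales concurrently at Week 4". Protocol 7.5.1 describes "the target population having a score of 2 or 3 (moderate or severe) at baseline" and observes that the two-point rule already contains the none-or-mild rule.

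The primary comparison in Protocol 7.5.1 is a CMH "test stratified by trial center using a two-sided test with a Type I error rate of 0.05". Protocol 7.5.5 adds: "Most of the efficacy endpoints are analyzed with trial center as a stratification factor". It also aims for at least 5 subjects per arm at each center and pools centers that fall short. SAP 4.9.1 reads, in full: "No adjustments for covariates are planned".

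Protocol 7.5 promises a point estimate and a confidence interval for the treatment difference. SAP 4.3 summarizes baseline IGA-FWS and PFWS by arm. No readable section brings baseline severity into the primary analysis or the randomization.

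**The concern.** The endpoint sets different finishing lines. On each scale, a baseline of 3 allows a final score of 0 or 1, while a baseline of 2 allows only 0. Both scales must meet the rule at once, so a subject scored moderate on even one scale faces the stricter requirement on that scale. A baseline value that decides how far a subject must go is likely to predict who responds.

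Using such a value in the estimate removes some variance from the treatment difference. It also corrects the estimate for any chance difference in severity mix between the arms. The readable plan does neither. If the SAP 4.3 table shows an imbalance, an adjustment made then would be post hoc. What is at stake is the precision of the estimate and the ease of interpreting it, not the validity of the test.

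**Working it through.** **The plan's own figure.** The sample size is 200 active and 100 placebo. It cannot be reproduced, because the response rates and power behind it are redacted. All rates below are assumptions.

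**Inputs from the documents.** n_A = 200, n_P = 100 (2:1), up to 15 centers, baseline 2 or 3 on each scale, two-sided 5% test.

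**Assumptions.** Share severe on both scales f = 50% to 70%. Active response is a3 in the severe group and a2 in the group moderate on at least one scale. Placebo response is b3 = 2% and b2 = 0%. The unadjusted estimate is taken as the crude difference, because the SAP text on the point estimate is not readable.

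**Step 1, variance.** Let w = f(1 − f), p_A = f·a3 + (1 − f)·a2, and p_P likewise.

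- Crude: V = p_A(1 − p_A)/200 + p_P(1 − p_P)/100
- Standardised: V_s = V − w(a3 − a2)²/200 − w(b3 − b2)²/100 + w[(a3 − a2) − (b3 − b2)]²/300

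Example with f = 0.60, a3 = 0.80, a2 = 0.40:

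- p_A = 0.64 and p_P = 0.012
- V = 0.64 × 0.36/200 + 0.012 × 0.988/100 = 0.0012706
- V_s = 0.0012706 − 0.24 × 0.16/200 − 0.24 × 0.0004/100 + 0.24 × 0.1444/300 = 0.0011931
- Ratio 0.939. Half-width 1.96√V falls from 6.99 to 6.77 points.

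**Step 2, effect of an imbalance.** If the severe share differs by d between arms, 2:1 allocation puts the active arm d/3 and the placebo arm 2d/3 away from the pooled share. The crude estimate moves by d[(a3 − a2)/3 + 2(b3 − b2)/3]. In the example with d = 10 points, this is 10 × (0.40/3 + 0.04/3) = 1.5 points.

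| f | a3 / a2 | Gap (points) | Variance ratio | Half-width, crude to standardised (points) | Shift for d = 10 (points) |
|---|---|---|---|---|---|
| 60% | 80% / 70% | 10 | 0.992 | 6.29 to 6.27 | 0.5 |
| 60% | 80% / 60% | 20 | 0.980 | 6.58 to 6.51 | 0.8 |
| 60% | 85% / 60% | 25 | 0.968 | 6.37 to 6.27 | 1.0 |
| 60% | 80% / 40% | 40 | 0.939 | 6.99 to 6.77 | 1.5 |
| 70% | 80% / 30% | 50 | 0.920 | 7.00 to 6.71 | 1.8 |
| 50% | 80% / 20% | 60 | 0.873 | 7.20 to 6.73 | 2.1 |

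In a wider grid with placebo rates up to 8%, the largest narrowing was 0.54 points (7.58 to 7.04).

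**Step 3, how likely is the imbalance?** Without stratification by severity, the SD of the between-arm difference at f = 60% is √[0.6 × 0.4 × (1/200 + 1/100)] = 0.06. A difference above 10 points then has probability about 0.075 to 0.10, for severe shares between 30% and 70%.

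**Step 4, test and power.** In 5,000 simulated trials per scenario (15 equal centers, no center effect), type I error stayed between 4.6% and 5.0% whether the CMH test was stratified by center, by baseline or by both. This held even with baseline strongly prognostic (40% versus 80%). With 200 and 100 subjects, power is 96.4% at 20% versus 5%, and about 100% from 40% versus 5% upward.

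**Step 5, crossing severity with center.** Fifteen centers by two severity groups make 30 strata, or 100/30 = 3.3 placebo subjects each on average. About 77% of strata had fewer than 5 placebo subjects. In low-rate stress tests, crossing lowered power from 84.9% to 83.0% and from 92.5% to 91.9%, compared with stratifying by center alone.

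**Step 6, coverage.** With placebo response at 0% to 2%, the 95% CI of the standardised difference covered about 94.6% to 94.7% of the time, so empty placebo strata did little harm.

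**The case against.** The strongest case against acting has four parts.

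First, a prespecified center-stratified test is legitimate and valid, power is probably ample, and no decision is likely to change. This stands, and it is why the priority is low.

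Second, much is hidden. SAP 4.6.1 survives only in fragments, which mention a sensitivity analysis and point estimates for the difference. Protocol 7.5.6 is partly redacted, and SAP 4.9.2 to 4.9.4 are not shown. A reader might infer that the plan ignores baseline severity altogether. The documents do not support that: baseline enters the endpoint as a change score and is tabulated by arm, and a severity subgroup or sensitivity analysis may lie under redaction. A hidden analysis would not, however, alter the readable SAP 4.9.1 or the readable primary test.

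Third, no randomization strata are readable. If severity is a stratification factor, the imbalance argument largely falls. The precision argument remains.

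Fourth, the remedy is not entirely clean. The interval would adjust for severity while the test adjusts for center. Placebo strata can also be empty: at 2% response, 40 placebo subjects yield no responder with probability 0.98^40, about 45%. The coverage result answers most of this, but the variance method must be written down.

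**Conclusion.** The point holds as a low-priority improvement. The treatment difference is not adjusted, in any readable text, for a recorded baseline value that the response rule makes likely to be prognostic. The gain is about 1% to 2% of variance for response gaps of 10 to 20 points and about 3% to 13% for gaps of 25 to 60 points. At most about half a percentage point comes off the CI half-width. A 10-point imbalance would move the estimate by about 0.5 to 2 points, against effects of roughly 50 to 75 points under the same assumptions. The sizes rest on assumed rates, and the imbalance figure also on randomization without severity strata.

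Two stronger readings go too far. A reader might infer that chance imbalance threatens the primary conclusion, but the simulated type I error and the size of the shift show otherwise. A reader might also infer that every responder endpoint is affected. The other endpoints are redacted, and the unequal target comes from the two-point rule, so the point extends only to endpoints that use that response.

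**What to change.** Before unblinding, amend SAP 4.9.1 and Protocol 7.5.1 as follows:

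- Prespecify a risk difference and 95% CI for the Week 4 2-point composite response, standardised over baseline severity in two groups: severe on both scales, and moderate on at least one.
- Apply the same adjustment to any other endpoint that uses the 2-point composite response.
- Keep the center-stratified CMH as the primary test, and do not cross severity with center.
- Name a variance method that copes with placebo strata without responders, and state that the interval and the test adjust for different factors.

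If a redacted section already provides a severity-adjusted estimate, a cross-reference from SAP 4.9.1 is enough. The cost is SAP and protocol wording and a few lines of code. No new data are needed.

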4.9.5. Data Handling Conventions

For all analyses, the protocol specified Treatment Day 0 will be referred to as Study Day 1.

4.10. Interim Analyses and Data Monitoring

No interim analysis is planned.
